#### **Contribution to overall strategy for TB vaccine development**

The ability to measure and quantify growth inhibition of BCG following a human challenge could provide a functional measure of anti-mycobacterial immunity induced by vaccination. This may be used to determine if potential biomarkers in peripheral blood that can be correlated with BCG growth inhibition. The development and validation of a controlled human infection model (CHIM) for TB would provide a significant new tool in the armoury of rational TB vaccine development.

The exploratory end-points of this study will contribute to a better understanding of the innate and adaptive immune response, both at a local respiratory mucosal level and systemically, following an acute *in-vivo* human mycobacterial challenge. A greater understanding of mucosal innate and adaptive immune constituents could help to develop interventions aimed at halting *M.tb* infection at the point of entry. Knowledge of this mucosal adaptive immune response may aid in vaccine development, as a successful vaccine candidate may alter or augment the immune response differently at a local level when compared with peripheral blood.

#### **4.5 Face-mask sampling**

We are collaborating with [name] team from the University of Leicester who have developed an adapted duckbill face mask containing a collection matrix. The matrix consists of strips of Polyvinyl Alcohol (PVA) for the purpose of collecting exhaled bacteria. A proof of concept case finding study in South Africa demonstrated that this PVA matrix technology detected pulmonary tuberculosis with a greater sensitivity than a contemporaneous sputum sample when performed at one time-point in symptomatic individuals and also appeared to detect disease at an earlier stage. (50) It would be an unfair burden to perform repeated bronchoscopies on individuals in an aerosol CHIM, however, collecting BCG recovery data at different time-points in an individual would allow further evaluation of the human clinical response to BCG. Assessing this method for BCG recovery against both BAL and induced sputum recovery of BCG could potentially facilitate an easier process for BCG recovery in future aerosol BCG CHIMs.

#### 4.6 BCG Challenge Study and COVID-19 Pandemic

In December 2019, a cluster of severe pneumonia cases of unknown aetiology was identified in Wuhan, China and was later confirmed to be due to a novel betacoronavirus. The virus was subsequently named SARS-CoV-2 due to its genetic similarity to the coronavirus responsible for severe acute respiratory syndrome (SARS-CoV). By January 2020, there was increasing evidence of human to human transmission and the number of cases of the new coronavirus disease, termed COVID-19, rapidly spread across the world. The World Health Organisation declared the outbreak of COVID-19 a pandemic on 11 March 2020 (43). As of 17th September 2021, there have been 7,406,017 confirmed COVID-19 cases and 135,314 deaths from COVID-19 in the United Kingdom(44).

Due to the aerosol route of delivery and need for respiratory monitoring and sampling, additional precautions will be implemented in this trial during the current COVID-19 outbreak.

There is currently very limited evidence available related to BCG and SARS-CoV-2 interaction. There is some interest in the potential non-specific innate immune system-boosting effects of BCG as a mechanism to reduce COVID-19 disease, but no current conclusive evidence and all ongoing studies into this effect are using ID BCG. Due to the lack of evidence and unknown interactions between BCG and SARS-CoV-2, we will exclude any volunteers who have had a laboratory confirmed (PCR or antibody) SARS-CoV-2 infection, evidence of current viral pneumonitis on chest radiograph or a high clinical suspicion of COVID-19 disease in the 3 months preceding enrolment.

During the pandemic SARS-CoV-2 testing will be undertaken 2 days (+/- 2 days) prior to enrolment and any participant who has a positive test would not be enrolled for at least 3 months. SARS-CoV-2 testing will also occur 2 days (+/- 2 days) prior to bronchoscopy. If positive, bronchoscopy will be postponed by at least 28 days from onset of symptoms (or test date if asymptomatic) as per British Thoracic Society guidelines (45). If this is not possible, the volunteer will not undergo bronchoscopy but may continue with other follow up visits at the discretion of the investigator once their self-isolation period has been completed. Immunology bloods tests will not be taken for 14 days from the onset of symptoms (or test date if asymptomatic) to minimise any infection risk.

Spirometry as a measure of pulmonary function will be routinely monitored at screening, day 0, day 2 and day 7, with additional transfer factor measured at screening and day 7.

If there is a significant drop in transfer factor ( $\geq 15\%$  from baseline or fall to below 80% predicted) (46), then this will be repeated at 3 months +/- 6 months if needed. Staff members will wear appropriate personal protective equipment (PPE). There has been no evidence of early or late allergic response to inhaled BCG in any of our trials and there has been no clinically significant sustained decrease in any spirometry parameters seen in any volunteer. Although, this is our first trial to administer aerosolized BCG to previously BCG vaccinated volunteers, a group in South Africa have recently administered  $10^4$  CFU BCG per bronchoscope in BCG-vaccinated and *M. Tuberculosis* latently infected subjects (47). This was well tolerated with no participants developing a significant adverse event or showing evidence of hypersensitivity reactions. Given this and the aerosol generating nature of the procedure, routine spirometry at all other visits will not occur. Spirometry may still be performed at any visit if at clinical discretion it is felt to be indicated and will occur using appropriate PPE. Induced sputum procedures are also aerosol generating. SARS-CoV-2 testing may be undertaken 2 days (+/- 2 days) prior to induced sputum procedures if required.

Any volunteers who test positive for current SARS-CoV-2 infection will be required to self-isolate as per the latest public health guidelines. As required by law, all results (whether positive or negative) and personal data (including volunteer name, contact details and postcode) will be shared with UK HSA. Asymptomatic volunteers undergoing planned SARS-CoV-2 testing will not be required to isolate whilst awaiting their results. All adaptations are in line with current UK government advice and may be modified in line with this advice if it changes in future.

If a volunteer is required to self-isolate, either due to their own symptoms/positive test or due to contact with a positive case, any routine study visits that cannot be postponed until after the isolation period will be conducted as far as possible by telephone/video call during the study window visit. A protocol deviation will still be completed for missed study samples. If safety bloods are due or there are any clinical concerns, a face-to-face visit may still be conducted at the discretion of the investigator.

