##### **Bronchoscopy Postponement criteria**

Bronchoscopy will not proceed on the scheduled day in any of the following situations:

- The volunteer has a temperature  $\geq 37.8^{\circ}\text{C}$
- The investigator judges the volunteer to have an acute moderate or severe illness (whether febrile or not)
- The investigator has any other concern that bronchoscopy may not be in the volunteer's best interests
- The volunteer has a positive SARS-CoV-2 PCR result or symptoms which the investigator considers to be highly consistent with COVID-19 disease since enrolment (unless had a negative PCR result at that time and symptoms have resolved).

In these cases, the volunteer may proceed to bronchoscopy at a later date (ideally next available), not undergo a bronchoscopy but continue with other follow up visits or be withdrawn from the study at the discretion of the investigator.

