#### **8.6 Diary Card**

Following the BCG challenge, volunteers will be asked to complete a diary card, which may be in paper or electronic format. Volunteers will be asked to record any specific solicited and unsolicited AEs daily, for 28 days. Diary cards will be reviewed with volunteers at the post-challenge follow up visits.

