#### 8.7.3.1 D0 Challenge

All movements of vials of the study agent in or out of the locked refrigerator will be documented. BCG accountability, storage, shipment and handling will be in accordance with local SOPs and other relevant local forms.

BCG will be administered by aerosol inhalation, according to the study-specific SOP. Volunteers will stay in the unit for 60 minutes ( $\pm 10$  minutes) after challenge. During the administration of BCG, monitoring equipment, oxygen, medicines including bronchodilators and resuscitation equipment will be immediately available for the management of anaphylaxis and bronchospasm according to the study-specific SOP.

In order to minimise dissemination of the BCG bacteria into the environment and to ensure the protection of staff, measures will be instituted during and following challenge to fully comply with local infection control and occupational health regulations.

Following challenge the following procedures will be undertaken:

The volunteers will be asked to wear a duckbill mask for another 30 minute period. Volunteers will be given an oral thermometer and a diary card to complete for 28 days with instructions on use, along with the emergency 24 hour telephone number to contact the on-call study physician if needed. Volunteers will be instructed on how to self-assess the severity of AEs. Specific solicited local and systemic AEs will be asked about. There will also be space in the diary card to self-document unsolicited AEs, and whether medication was taken to relieve any symptoms. If bronchoscopy is postponed, a further diary card may be utilised to ensure AEs for 7 days post bronchoscopy are captured.

Diary cards will collect information on the timing and severity of the following solicited AEs:

Local (respiratory) solicited AEs	Systemic solicited AEs
Cough (any cough)	Documented Fever (oral temp $>37.5^{\circ}\text{C}$ )
Coughing up phlegm	Feverishness
Coughing up blood	Joint pains (arthralgia)
Wheeze	Muscle pains (myalgia)
Shortness of breath	Fatigue
Sore throat	Headache
Tickly throat	Malaise
Chest tightness	Nausea
Chest pain	

Table 3. Solicited AEs as collected in post challenge diary cards.

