#### **8.7.5 Bronchoscopy visit – 2 days**

Volunteers will be tested for SARS-CoV-2 during pandemic period.

Table 4: Schedule of visits

Visit number	1	2	3	4	5	6	7	8	9	10	11	12	13
Timeline (days)*	Screen	-2	0	2	7	B-2	14	IS-2	28	56	84	IS-2	168
Time windows (days)		±2		±1	±2	±2	-5 to +21	±2	-7 to +14	±14	±21	±2	±28
Inclusion/exclusion criteria	X												
Review contra-indications	X		X				X						
Informed consent	X						X						
Medical history	X		(X)	(X)	(X)		(X)		(X)	(X)	(X)		(X)
Physical examination	X		(X)	(X)	(X)		(X)		(X)	(X)	(X)		(X)
Vital signs	X		X	X	X		X		X	X	X		X
Urinalysis	X												
PFTs	X		X	X	X		(X)		(X)	(X)	(X)		(X)
β-HCG urine test (females only)	X		X				X						
SARS-CoV-2 test**		X				X		(X) +					(X) +
BCG Challenge			X										
Bronchoscopy							X						
Chest radiograph	X												
Mask wearing			X	X	X		X		X				X
Induced Sputum Procedure ^									(X)				(X)
Local & systemic events			X	X	X		X		X	X	X		X
Diary card setup			X				(X)						
Diary card final review									X				
Biochemistry (U+Es, LFTs)	3		3		3		3		3				
Haematology (FBC)	2		2		2		2		2				
Coagulation (PT, APTT)	3												
HBV, HCV, HIV	5												
TB IGRA	6												
HLA typing			4										
Exploratory immunology			60	60	60		60		60	60	60		60
Blood vol per visit (mL)	19		69	60	65		65		65	60	60		60
Cumulative blood vol (mL)%	19		88	148	213		278		343	403	463		523

\* Timeline is approximate, exact visit timings ( $\pm$  windows periods) relate to actual (not intended) date of previous visit  
 X Event scheduled to occur B-2 = bronchoscopy -2 days IS-2 = Induced Sputum -2 days

(X) If considered necessary, emphasising any complaint or change in medication

\*\* During COVID-19 pandemic (X) If considered necessary based on current COVID-19 regulations.

+May be lateral flow test or PCR

^ may be undertaken depending on resources and current COVID-19 situation. SARS-CoV-2 testing may be undertaken prior to induced sputum.

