#### 10.4 Reporting Procedures for All Adverse Events (see local SOP for AE reporting)

All AEs occurring in the 14 days following challenge and the 14 days following bronchoscopy observed by the investigator or reported by the volunteer, whether or not attributed to BCG, will be recorded on the diary card. Data from the diary cards will be extracted following the last volunteer last visit (LVLV) or at any time prior to this in order to perform an interim safety analysis. Outside the diary periods, respiratory and systemic AEs (listed in 6) will be specifically solicited at each visit, and graded by severity (as detailed in section 9.5). All AEs starting after the diary period(s), or persisting after this period, will be recorded in the AE line listing of the CRF.

Recording and reporting of all AEs will take place as detailed in SOP VC027 Adverse Event Data Collection and Analysis. All AEs that result in a volunteer's withdrawal from the study will be followed up until a satisfactory resolution occurs, or until a non-study related causality is assigned (if the volunteer consents to this). SAE will be collected throughout the entire study period.

Adverse event	
Respiratory	Cough
	Sore throat
	Tickly throat
	Wheeze
	Shortness of breath
	Coughing up phlegm
	Coughing up blood
	Chest tightness
	Chest pain
Systemic	Documented fever (oral temperature > 37.5° C)
	Myalgia
	Arthralgia
	Feverishness
	Headache
	Fatigue
	Nausea
	Malaise

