## 12. DATA MANAGEMENT

### 12.1 Data Handling

The Chief Investigator will be responsible for all data that accrues from the study.

The data will be captured directly into the volunteers' electronic CRFs or transferred from a paper source in to the eCRF created on the study specific database designed using OpenClinica™ (an open source clinical trial software for Electronic Data Capture (EDC)). Electronic data will be stored on secure servers, which are outsourced by OpenClinica™. Data will be entered directly into the study database via a web browser using encrypted ([https](https://)) transfer. OpenClinica™ meets FDA part 11B standards. This includes safety data, laboratory data and outcome data.

All adverse event data (both solicited and unsolicited) reported by the volunteer will be entered onto a volunteer's electronic diary card for a maximum of 14 days following the administration of BCG and 14 days following the bronchoscopy. The Diary provides a full audit trail of edits and will be reviewed at each review time-points indicated in the schedule of events. Any adverse event continuing beyond the period of the diary will be copied into the eCRF (OpenClinica) and followed to resolution, if there is a causal relationship to BCG, or to the end of the study if there is no causal relationship.

The participants will be identified by a unique study specific number and code in any database. The name and any other identifying detail will NOT be included in any study data electronic file.

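### The 28-day diary meets the plan's own 14-day post-bronchoscopy AE rule only if bronchoscopy is done by D14; for a later one, a further card is optional and set at 7 days.

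*Combined protocol and SAP*

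**What the plan says.** Four places set how long AEs are recorded daily.

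- Section 8.6 sets one card from challenge: "Volunteers will be asked to record any specific solicited and unsolicited AEs daily, for 28 days".
- Section 10.4 names what goes on the diary card: "All AEs occurring in the 14 days following challenge and the 14 days following bronchoscopy". The sentence is mandatory and makes no exception for a late bronchoscopy.
- Section 12.1 repeats the two periods for the electronic diary, as an upper limit: "for a maximum of 14 days following the administration of BCG and 14 days following the bronchoscopy".
- Section 8.7.3.1 deals with the late case: "If bronchoscopy is postponed, a further diary card may be utilised to ensure AEs for 7 days post bronchoscopy are captured".

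Table 4 (under 8.7.5) marks diary set-up at the bronchoscopy visit in brackets, meaning only if considered necessary. It gives that visit a window of −5 to +21 days, nominally D9 to D35. Its footnote says that visit timings "relate to actual (not intended) date of previous visit".

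Bronchoscopy can also move beyond that window. Under the postponement criteria in 7.3.4, "the volunteer may proceed to bronchoscopy at a later date (ideally next available"), with no latest date given. Section 4.6 adds a minimum delay after a positive swab: "bronchoscopy will be postponed by at least 28 days from onset of symptoms (or test date if asymptomatic"). The same section fixes when the swab is taken: "SARS-CoV-2 testing will also occur 2 days (+/- 2 days) prior to bronchoscopy".

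**The concern.** AEs and symptom profiles are the secondary endpoint (section 5), and bronchoscopy itself causes many of the solicited symptoms. Appendix A reports, for the two earlier aerosol studies, cough after bronchoscopy in 86% of volunteers with a mean duration of 5 days, and documented fever within 48 hours in 9.7%.

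Site staff who follow 8.6, 8.7.3.1 and the bracketed mark in Table 4 can comply with all three and still miss the 14 days that 10.4 requires. Two volunteers at the same dose could then have different lengths of daily recording after the same procedure, only because one was bronchoscoped later. With three volunteers per dose, that makes symptom profiles harder to compare.

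Section 8.7.3.1 also applies only when bronchoscopy is postponed. One first booked late but inside the window gets no further card under its wording.

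**Working it through.** **Inputs.** Card length 28 days from challenge (8.6). Post-bronchoscopy period 14 days (10.4; a maximum in 12.1) or 7 days (8.7.3.1). Window D9–D35 on nominal days (Table 4). Swab 0 to 4 days before bronchoscopy, and a deferral of at least 28 days (4.6). I take the card as ending on D28; if D0 counts as the first diary day, each figure for days left that is above zero falls by one.

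**Where the 28 days fits.** 14 days after challenge plus 14 days after a bronchoscopy on D14 gives 14 + 14 = 28. The card length and the 14-day rule agree exactly for an on-time bronchoscopy.

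**Other days.** For a bronchoscopy on day P, days left on the card = max(0, 28 − P). The shortfall against a rule of R days is R minus the days left, or 0 if that is negative.

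| Bronchoscopy day P | Days left on card | Short of 14 | Short of 7 |
|---|---|---|---|
| D9 | 19 | 0 | 0 |
| D14 | 14 | 0 | 0 |
| D15 | 13 | 1 | 0 |
| D21 | 7 | 7 | 0 |
| D22 | 6 | 8 | 1 |
| D28 | 0 | 14 | 7 |
| D35 | 0 | 14 | 7 |
| D38–D42 | 0 | 14 | 7 |

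The nominal window has 35 − 9 + 1 = 27 days. The card falls short of 14 days on D15–D35 (21 days), falls short of 7 days on D22–D35 (14 days), and has ended on D28–D35 (8 days). These count permitted days and say nothing about how likely each booking is. The days left depend only on the actual day P, so the choice of window anchor does not alter them.

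**The COVID example.** A bronchoscopy booked for D14 has its swab on D10 to D14. If the volunteer is positive and asymptomatic, the earliest new date is 10 + 28 = D38 to 14 + 28 = D42. That is 10 to 14 days after the card ends, and 3 to 7 days past the nominal D35. Symptom onset by D7 gives 7 + 28 = D35 or earlier, back inside the window. With onset from D0 to D7 the new date is D28 to D35, when the card is still exhausted.

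The documents give no rate of positive swabs. At an assumed 1–5% with all 12 volunteers swabbed, the expected number is 12 × 0.01 = 0.12 to 12 × 0.05 = 0.6 volunteers, and fewer if testing stops.

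**What remains without a second card.** Section 10.4 has the listed respiratory and systemic AEs solicited and graded at each visit outside the diary periods. Under Table 4's footnote, the visit after bronchoscopy is the D28 visit, due 28 − 14 = 14 days after the actual procedure. With its window of −7 to +14 days, that is 7 to 28 days after. The mean cough of 5 days would be over before the earliest of these, so its timing and severity would rest on recall.

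**The case against.** The strongest reply is that 8.7.3.1 is the specific rule for late bronchoscopies and works as intended. The 28-day card already gives 7 days for any bronchoscopy up to D21, which explains why the further card is optional. Section 12.1's 14 days is a ceiling that 7 days does not breach. A mean cough of 5 days and fever within 48 hours do not show 7 days to be too short. All of this stands as a case that 7 days could be a sensible choice. It does not reconcile 8.7.3.1 with 10.4, which is mandatory at 14 days. Nor does it cover D22 onwards, where the card gives fewer than 7 days and the further card stays optional.

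On the COVID route, 4.6 says a volunteer whose bronchoscopy cannot be so postponed will not have one, and 8.7 says visits take place within their windows. Together these can be read as dropping an out-of-window procedure, and 13.3 would log one done anyway as a deviation. That reading is open, so D38–D42 is only an example. The gap inside the window remains under it.

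Three stronger inferences are tempting, and the documents do not support them.

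- *Post-bronchoscopy AEs would go unrecorded.* Section 10.4 still requires solicitation at visits and a CRF listing of later events. Daily detail is at risk, not the events themselves.
- *The next contact after a D38–D42 bronchoscopy would be D56.* The Table 4 footnote ties timings to the actual previous visit, which gives about 14 days after the procedure.
- *The primary endpoint is compromised because no rule says whether a late sample is summarised with D14.* The study is descriptive, and section 11 promises a SAP before data lock that can settle the display.

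**Conclusion.** The inconsistency is real but minor. For any bronchoscopy after D14, the 28-day card alone falls short of the plan's 14 days of daily post-bronchoscopy recording, by 1 day at D15, 7 at D21 and all 14 from D28. The only provision for a further card is discretionary, covers half the period and is limited to postponed procedures.

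This rests on reading 10.4 as applying to every bronchoscopy, as it is worded, and on the card ending at D28. It does not depend on any infection rate. How often it would arise is unknown: ordinary late bookings and postponements for fever or illness under 7.3.4 can meet it, while the COVID route is probably rare. It affects the detail and comparability of the secondary safety data. It does not affect the detection of serious events, which 10.4 collects throughout the study.

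**What to change.** In 8.7.3.1, state that for any bronchoscopy more than 14 days after challenge, whether postponed or first booked late, a further diary card is issued so that AEs are recorded daily for 14 days after the procedure. In Table 4, make the second diary set-up required in that case. Fourteen days agrees with 10.4 and gives late volunteers the same cover as those bronchoscoped on D14.

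If 7 days is what the sponsor intends, correct 10.4 and 12.1 instead. The further card should then still be required from D22, where the first card gives fewer than 7 days.

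The cost is min(14, P − 14) extra diary days for a volunteer bronchoscoped on day P after D14, so at most 14, plus a protocol amendment through the section 15.3 process. No extra challenge, bronchoscopy, visit or blood is needed. The 28-day deferral and the visit window can stay as they are.
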